#### **8.4.3.1 Assessment of fertility**

A woman is considered of childbearing potential from menarche and until becoming post-menopausal unless permanently sterile. Permanent sterilization methods include hysterectomy, bilateral salpingectomy and bilateral oophorectomy. Medical documentation of oophorectomy, hysterectomy, or tubal ligation must be retained as source documents.

A postmenopausal state is defined as no menses for 12 months without an alternative medical cause and an appropriate clinical profile.

In absence of the medical documentation confirming permanent sterilization, or if the post-menopausal status is not clear, the investigator should use laboratory testing (FSH) and medical judgment to appropriately evaluate the fertility state of the woman and document it in the source document.

#### 8.4.4 Appropriateness of safety measurements

The selected safety monitoring assessments (including laboratory assessments covering clinical chemistry, hematology, coagulation status and immunoglobulins, as well as clinical and physical assessments, triplicate ECG monitoring and general AE assessments) are reliable and well-established standard measures which allow valid and close safety monitoring of the trial's patient population, with regards to their disease, to the compound they are treated with, remibrutinib, and also to their overall medical safety.

In addition to safety assessments that are standard in this population, participants are not eligible to join the study if they have a history of a severe or life-threatening hypersensitivity event needing an ICU admission or intubation within 60 days prior to Screening Visit 1 or uncontrolled asthma at Screening Visit 1. Spirometry is performed in asthmatic participants before each DBPCFC for safety purposes.

Also, study treatment will be discontinued if the participant experiences a life-threatening hypersensitivity event needing an ICU admission or intubation OR a serious hypersensitivity event suspected to be related to study treatment.

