2. **Treatment period:** The treatment period is approximately one month long and can range from 4-5 weeks due to the visit windows allowed as well as due to the need to collect end-of-treatment data across 3 visits that have required minimum spacing between them.

Study participants will be seen in the clinic on Day 1 (treatment randomization), Day 8, and Day 22, for on-treatment clinic visits and drug dispensation. Study participants will also be seen in the clinic for three end-of-treatment visits, which collect primary and secondary one month endpoint data, collectively. These will occur on Day 25, Day 26 (DBPCFC part 2A) and Day 28 (DBPCFC part 2B).

The study treatment will begin on Day 1 at the randomization visit and will continue until the CCI of the DBPCFC part 2B end-of-treatment visit. The study treatment is three placebo -matched tablets administered by the participant at home CCI

Participants will continue study drug dosing CCI from Day 1 visit through the CCI dose of their Day 28 (DBPCFC part 2B) visit. The CCI administration of study drug on Day 28 (DBPCFC part 2B) will be the last dose.

There is a minimum of 2 days (48 hours) needed between the DBPCFC parts 1 and 2. Given the need for flexibility to accommodate holidays and weekends, participants will have a window of plus 2 days for all three end-of-treatment visits on Days 25, 26 and 28, which, if maximized, may extend treatment to up to 34 days. Treatment will not exceed 34 days. Participants will be encouraged to try to maintain the visit schedule as written and avoid utilizing windows as much as possible to keep the study treatment period as short as possible.

3. **End of Study Visit and Follow Up Period:** After completion of Day 28 (DBPCFC part 2B) visit, participants will return to clinic 3 days post-last-dose on Day 31 for the end of study visit, which will include post-dose assessments and study evaluations including safety, pharmacokinetics, post-treatment biomarkers, etc. (See [Table 8-1](#)). The end-of-study visit should not be earlier than 3 days (72 hours) after the last dose of study drug to facilitate proper PD/biomarker analysis. Additionally, a 30-day post-last-dose safety call will be placed to the participant and will complete participation in the study.

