## 6.2.2 Prohibited medication

Use of the treatments displayed below ([Table 6-4](#)) is not allowed from Screening Visit 1 to the completion of all three end-of-treatment visits (Day 28). The minimum required period without prohibited treatment before Screening Visit 1 is also shown.

If a participant develops a medical condition that requires use of prohibited treatment or if participant exhibits a behavior of non-compliance regarding prohibited medications at any timepoint from Screening Visit 1 to the end of the completion of all three end-of-treatment visits (Day 28), investigational treatment and DBPCFC must be discontinued (see also [Section 9.1.1](#)).

As described above, remibrutinib is metabolized mainly by CYP3A4. Therefore, concomitant administration of remibrutinib with drugs that are strong and moderate CYP3A4 inhibitors is prohibited to avoid increases in the systemic exposure up to 4-fold. Although no DDI study has been conducted so far with CYP3A4 inducers, likewise, concomitant administration of remibrutinib with drugs that are moderate and strong CYP3A4 inducers is prohibited as a published SimCYP model predicts a 90% decrease in remibrutinib blood exposure which can lead to a total loss of efficacy.

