## **9 Discontinuation and completion**

### **9.1 Discontinuation from study treatment and from study**

#### **9.1.1 Discontinuation from study treatment**

Discontinuation of study treatment for a participant occurs when study treatment is stopped earlier than the protocol planned duration and can be initiated by either the participant or the investigator. The investigator must discontinue study treatment for a given participant if he/she believes that continuation would negatively impact the participant's well-being.

Study treatment must be discontinued under the following circumstances:

- Participant decision
- Pregnancy
- Any SAE, with the exception of anaphylaxis unrelated to study drug, and which does not require hospital admission for  $\geq 24$  hours.
- Any severe AE that is assessed to be at least possibly related to study drug
- Any moderate to severe infection
- Participant requires use of prohibited treatment as per [Section 6.2.2](#)
- Participant failure to comply with the study protocol results in potential risk to the participant
- Participant experiences a moderate or severe hypersensitivity event unrelated to the DBPCFC and suspected to be related to study treatment
- Confirmed QTcF  $> 500$  msec
- Abnormal liver laboratory results requiring discontinuation (see [Section 16.2](#))
- Abnormal renal laboratory results requiring discontinuation (see [Section 16.3](#))
- Platelets  $< 75,000/\text{mm}^3$
- Clinically significant spontaneous bleeding events
- Any other adverse event or laboratory abnormality that in the judgment of the investigator prevents the participant from safely continuing in the study
- Any protocol deviation or other situation that results in a significant risk to the participant's safety

If discontinuation of study treatment occurs, the investigator should make a reasonable effort to understand the primary reason for the participant's premature discontinuation of study treatment and record this information. If treatment code has been broken as noted in [Section 6.5](#) and [Section 6.7.3](#), and site personnel and sponsor determine discontinuation of study treatment is indicated, this information should be recorded. The investigator must also contact the IRT to register the participant's discontinuation from study treatment.

**All participants who discontinue from study treatment prematurely should complete the End of Study visit at the time of treatment discontinuation.**

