### **9.1.2 Discontinuation from study**

Discontinuation from study is when the participant permanently stops receiving the study treatment, and further protocol-required assessments or follow-up, for any reason.

Discontinuation of treatment prior to completion of the three end-of-treatment assessment visits: Participants who discontinue treatment prior to Day 26 (DBPCFC Part 2A) due to any reasons other than adverse event OR who miss more than 20% of study doses throughout the study treatment period OR who miss ANY medication doses for  $\geq 3$  consecutive days in the seven days prior to Day 26 (DBPCFC Part 2A) will not undergo end-of-treatment DBPCFC part 2A or 2B. Those participants who discontinue treatment after an adverse event, but who resume therapy after discussion between investigator and sponsor, AND who have not missed more than 20% of study doses throughout the treatment period AND have not missed ANY medication doses for  $\geq 3$  consecutive days in the seven days prior to end-of-treatment DBPCFC Part 2A (Day 26) WILL undergo end-of-treatment DBPCFC, Part 2A and 2B. Participants who discontinue due to noncompliance of study treatment may be replaced after discussion with Novartis.

If the participant agrees, the three end-of-treatment visit(s) and/or the end-of-study visit should be conducted at the time of the participant's study discontinuation, as detailed in the assessment table (refer to [Section 8](#)).

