#### 10.1.4 SAE reporting

To ensure participant safety, every SAE, regardless of causality, occurring after the participant has provided informed consent and until 30 days after the last study visit must be reported to Novartis safety immediately, without undue delay, but under no circumstances later than within 24 hours of obtaining knowledge of the events (Note: if more stringent, local regulations regarding reporting timelines prevail). Any SAEs experienced after the 30 day period should only be reported to Novartis Safety if the investigator suspects a causal relationship to study treatment, unless otherwise specified in local regulations. Any SAEs reported up to the participant's last visit will be reported in the eCRF. SAEs beyond that date will only be recorded in the Novartis Safety database. Detailed instructions regarding the submission process and requirements are to be found in the investigator folder provided to each site.

Information about all SAEs is collected and recorded on the electronic Serious Adverse Event Report Form (eSAE) (with paper backup if required); all applicable sections of the form must be completed in order to provide a clinically thorough report.

1. Screen Failures (e.g. a participant who is screened but is not treated or randomized): SAEs occurring after the participant has provided informed consent until the time the participant is deemed a Screen Failure must be reported to Novartis with 24 hours of learning of its occurrence.
2. Randomized OR Treated Participants: SAEs collected between time participant signs ICF until 30 days after the participant has discontinued from study treatment.

All follow-up information for the SAE including information on complications, progression of the initial SAE and recurrent episodes must be reported as follow-up to the original episode immediately, without undue delay, but under no circumstances later than within 24 hours of the Investigator receiving the follow-up information (Note: if more stringent, local regulations regarding reporting timelines prevail) of the investigator receiving the follow-up information. An SAE occurring at a different time interval or otherwise considered completely unrelated to a previously reported one must be reported separately as a new event.

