#### **14.1 Protocol amendments**

Any change or addition to the protocol can only be made in a written protocol amendment that must be approved by Novartis, health authorities where required, and the IRB/IEC prior to implementation.

Only amendments that are required for participant safety may be implemented immediately provided the health authorities are subsequently notified by protocol amendment and the reviewing IRB/IEC is notified.

Notwithstanding the need for approval of formal protocol amendments, the investigator is expected to take any immediate action required for the safety of any participant included in this study, even if this action represents a deviation from the protocol. In such cases, Novartis should be notified of this action and the IRB/IEC at the study site should be informed according to local regulations.

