## **16.4 Appendix 4: Double-blind Placebo-Controlled Food Challenge (DBPCFC)**

### **16.4.1 Background**

The DBPCFC represents the gold standard to diagnose food allergy. It is also the most objective method to clinically estimate threshold doses for allergenic foods in highly sensitive individuals ([Taylor et al 2004](#)). In this study the DBPCFC is based upon two available guidelines, PRACTALL ([Sampson et al 2012](#)) and the CoFAR Grading Definition of Dose-Limiting Symptoms. The double-blind aspect of the DBPCFC markedly reduces any potential bias of participant and/or supervising health care professionals that could interfere with its appropriate interpretation. The test itself corresponds most closely to the natural ingestion of food.

The DBPCFC is to be strictly performed under medical supervision to document the dose of allergen that provokes a reaction and, if needed, to administer symptomatic treatment which could potentially require the management of anaphylaxis. Participants must be in good health before proceeding with the food challenge and should be advised to avoid physical exercise at least one hour prior to the start of the procedure. A light breakfast is optional on the day of the DBPCFC, in line with local practice. Additionally participants should be on minimal or no symptomatic medication before starting the DBPCFC ([Table 6-2](#) and [Table 6-3](#)). Due to the inherent risk of a severe reaction, participants who have experienced a severe or life-threatening hypersensitivity event leading to ICU admission or intubation within 60 days prior to Screening Visit 1 are excluded from study participation.

Intravenous access may be set up before the DBPCFC at the investigator's discretion (e.g., participant at high risk of reaction or severe reaction based upon prior history and medical history).

At the start of the DBPCFC a small dose of peanut allergen is administered. This dose is intentionally lower than any dose expected to induce a reaction ([Niggemann, Beyer 2007](#)). While monitoring the participant for any allergic symptoms, the allergen dose is gradually increased until a cumulative dose at least equivalent to the portion of allergen as defined in the objectives ([Section 2](#)) is ingested (refer to the LOU064I2201 Pharmacy Manual).

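### The anaphylaxis exception in Protocol 9.1.1 lacks the ICU or intubation limit that Protocol 8.4.4 already sets for stopping study drug

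*Protocol*

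**What the plan says.** **Protocol 8.4.4** says study drug will be stopped if the participant has a "life-threatening hypersensitivity event needing an ICU admission or intubation OR a serious hypersensitivity event suspected to be related to study treatment". The capitalised OR separates two limbs, and the relatedness condition sits in the second.

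**Protocol 9.1.1** lists when study drug must be stopped. Its SAE bullet reads "Any SAE, with the exception of anaphylaxis unrelated to study drug, and which does not require hospital admission for" 24 hours or more. The exception is limited by cause and length of stay only; it mentions neither intensive care nor intubation. The section also says that participants who stop study drug have no further food challenges.

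**Protocol 9.1.2** (and 6.7.1 in the same terms) deals with resumption: "Those participants who discontinue treatment after an adverse event, but who resume therapy after discussion between investigator and sponsor", and who stay within the missed-dose limits, do undergo parts 2A and 2B of the challenge. The limits are more than 20% of doses overall, or three or more consecutive days in the seven days before part 2A.

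**SAP 1.2.1** defines the primary population as participants who underwent both parts, 2A and 2B. Protocol 2.1 refers to the one-month challenge without naming the two parts.

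**The concern.** Section 9.1.1 is where a site looks for stopping rules; 8.4.4 is a section on whether the safety measurements are appropriate. Neither refers to the other. For one kind of event the 9.1.1 SAE bullet steps aside, while 8.4.4 requires a stop: anaphylaxis not related to study drug, treated in intensive care or with intubation, and discharged within 24 hours.

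The version that matters is a reaction to accidental exposure before the peanut part of the end-of-treatment challenge. Protocol 10.2.3 acknowledges that accidental exposures happen. Because stopping study drug is what cancels the remaining challenges, a site that relied on the SAE bullet could keep the participant on drug and deliberately expose them to peanut again. The protocol itself treats such an event as a marker of risk: in 16.4.1, "Due to the inherent risk of a severe reaction, participants who have experienced a severe or life-threatening hypersensitivity event leading to ICU admission or intubation" in the 60 days before Screening Visit 1 are kept out of the study.

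A second, separate issue concerns the analysis. If any safety stop falls between parts 2A and 2B and peanut was given at 2A, the primary outcome has been observed but the participant no longer meets the SAP's population definition. The outcome is then lost because of the reaction that helped determine it.

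**Working it through.** **A. The two stopping rules on one test case.** The plan gives no figure to reproduce, so the check sets the rules side by side. Test case: anaphylaxis unrelated to study drug, ICU admission or intubation, hospital stay under 24 hours, before the peanut challenge.

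- 8.4.4, ICU/intubation limb: met. Stop.
- 9.1.1, SAE bullet: a life-threatening event is an SAE (10.1.3), but the exception applies. No stop from this bullet.
- 9.1.1, severe AE bullet: needs at least possible relation to study drug. Not met.
- 9.1.1, hypersensitivity bullet: needs suspected relation to study treatment. Not met.
- 9.1.1, prohibited-treatment bullet: 6.2.2 ends both drug and challenge "If a participant develops a medical condition that requires use of prohibited treatment". Section 6.2.3 allows epinephrine, SABA, antihistamines, short corticosteroid bursts and saline as rescue. Whether other ICU care would count depends on Table 6-4, which is redacted. Undetermined.
- 9.1.1, opening duty, other-AE bullet and significant-risk bullet: can all reach the case. The opening duty turns on the investigator's belief and the other-AE bullet on the investigator's judgement. The significant-risk bullet has no such wording, but someone must still assess the risk.

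If the stay is 24 hours or more, or the event is related to study drug, both sections require a stop. The mismatch is confined to the test case.

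**Would missed doses keep the participant out of the challenge?** One lost day of 28 is 1/28 = 3.6% of dosing days, against a limit of 20% (0.20 × 28 = 5.6 days), and one day is fewer than three consecutive days. A stay under 24 hours does not by itself breach either limit.

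**Where in the schedule it matters.** If peanut is given at 2A and the reaction occurs there, only the placebo part remains. If peanut is given at 2B, dosing and challenges are over. The exposure concern is therefore limited to events before the peanut part.

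**B. The SAP population.** Inputs: n = 14 to 16 completers per one-month arm (Protocol 12.8); a response rate of 80% on remibrutinib (Amendment 02 rationale); one affected participant in the arm, which is an assumption. Responders r are the whole number nearest 0.8n: 11.2 gives 11, and 12.8 gives 13. Dropping a non-responder gives r/(n−1); dropping a responder gives (r−1)/(n−1).

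- n = 14: 11/14 = 78.6%. Non-responder dropped: 11/13 = 84.6% (+6.0 points). Responder dropped: 10/13 = 76.9% (−1.6).
- n = 16: 13/16 = 81.3%. Non-responder dropped: 13/15 = 86.7% (+5.4). Responder dropped: 12/15 = 80.0% (−1.25).

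Both directions are possible under the dosing schedule in 16.4.3: a reaction at 600 mg or below makes a non-responder, while one at 1000 or 3000 mg comes after 600 mg was tolerated.

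**The case against.** The strongest reply is that the sections do not conflict. The 9.1.1 exception takes an event out of one bullet; it does not permit continuing, and the list is not said to be exclusive. 8.4.4 is mandatory in its own right. This stands. A reader might infer that 9.1.1 overrides 8.4.4, or that the plan allows drug after intubation; the text supports neither.

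The surrounding safeguards are also real. The opening duty and significant-risk bullet of 9.1.1 compel a stop once their conditions are met. Section 16.4.1 requires good health before a challenge. Sections 6.6 and 9.1.2 bring the sponsor into any interruption or resumption. The event is an SAE, to be reported "under no circumstances later than within 24 hours of obtaining knowledge of the events", so the sponsor should normally know of it before the challenge. On the resumption route, the sponsor would have to overlook its own rule. What survives is that none of these states the ICU/intubation limit, and a participant whose drug was never interrupted would simply stay on the visit schedule.

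Two tempting arguments should not be used. First, since "Treatment will not exceed 34 days", an event on Day 1 or later falls at most 33 days (34 − 1) before the last possible challenge, and a reader might set that against the 60 days in the exclusion criterion. That is an entry rule counted back from Screening Visit 1; no on-treatment rule uses 60 days. Second, a reader might infer that such a participant would be given 3000 mg. Dosing starts at 1 mg and rises in nine steps, and the next dose is forbidden after any dose-limiting symptom, so only someone who tolerates every lower dose gets there.

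It could also be said that the relatedness condition in 8.4.4 governs both limbs, which would remove the mismatch. The capitalised OR makes that the less natural reading.

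On the SAP point, requiring both parts of a placebo-controlled challenge is a defensible choice. But primary responder status depends only on tolerance of peanut, so the placebo part is not needed to determine it.

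**Conclusion.** The concern holds in a narrow form and is a low-priority correction. The operative stopping list excepts an event for which another section of the same protocol requires a stop. It needs unrelated anaphylaxis, ICU care or intubation, a stay under 24 hours, timing before the peanut challenge, and a site that applies the SAE bullet alone while the other safeguards do not take effect. The case is rare, and the documents give no rate. The finding rests on reading the relatedness condition in 8.4.4 as belonging to its second limb, and it could shrink further if redacted Table 6-4 covers ICU treatments.

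The SAP issue is minor and independent. A reader might take the shifts of +6.0 to −1.6 points as the size of the stopping-rule problem; they come from the SAP's population wording, apply to any safety stop between 2A and 2B, and assume one such participant in an arm of 14 to 16 with a response rate near 80%.

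**What to change.** **Protocol.** In the 9.1.1 SAE bullet, add to the anaphylaxis exception: *and does not need ICU admission or intubation*. Cross-reference 8.4.4 and 9.1.1 to each other. This adds no procedures and only states in the operative list a limit the sponsor has already set. It does need a written amendment, which "must be approved by Novartis, health authorities where required, and the IRB/IEC prior to implementation", so it should go into the next one rather than prompt one of its own.

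**SAP (separate, optional).** State in 1.2.1 that a peanut outcome observed at part 2A is counted when a safety stop cancels part 2B. This changes the primary population for any participant stopped between the two parts. The downside is that such a participant has no placebo challenge and cannot be evaluated for supplementary estimand 4. Without the change, supplementary estimand 2 gives partial cover if losing 2B counts as missing the challenge, but it would score the participant as a non-responder even if 600 mg had been tolerated at 2A.
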